6.2 Anticipated Duration of the Clinical Investigation

Study duration is anticipated to be approximately 4 months.

6.3 Evaluation Criteria / Effectiveness and Safety

6.3.1 Primary Clinical Endpoint

The number of insertion attempts (any forward movement of the needle following puncture of the skin) in the study device group as compared to the control group (palpation). Attempts are counted until confirmation of spinal canal access can be assessed.

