Study Duration	Study duration is anticipated to be approximately 4 months
Study Center(s)	Approximately 3 sites in the United States
Objectives	The primary objective of this study is to establish the superiority of VerTouch versus the conventional palpation technique for the number of insertion attempts required in diagnostic and therapeutic neuraxial procedures.
Number of Subjects	It is expected that approximately 120 subjects will be screened to meet a target enrollment goal of 96 subjects.
Main Inclusion / Exclusion Criteria	Inclusion Criteria 
1. Males and females aged 18 years and above, inclusive2. Subjects scheduled for one of the following procedures:
• Diagnostic LP (collection of CSF and/or measurement of ICP to diagnose hemorrhaging or neurological infections)• Therapeutic LP (intrathecal injection of therapeutic agents; drainage of CSF to treat pseudotumor cerebri)• Planned orthopedic or obstetric procedure, such as labor/induction, cesarean section,

hysterectomy, or total hip/knee replacement, with neuraxial anesthesia (injection of anesthetic into spinal and/or epidural space to reduce pain during procedure)

- Epidural blood patch (use of autologous blood to close holes in the dura mater and relieve PDPH)
- 3. Subjects having a BMI $\leq 42\text{kg}/\text{m}^2$

Exclusion Criteria

1. Patient does not provide informed consent
2. Skin or soft tissue infection near the puncture site
3. Allergy to local anesthetic
4. Uncorrected coagulopathy
5. Acute spinal cord trauma
6. History of lumbar spinal surgery
7. Prior known failed neuraxial anesthesia
8. Diagnosed scoliosis, thoracic kyphosis, lumbar lordosis, scleroderma, or ankylosing spondylitis, or lumbar spinal stenosis
9. Incarcerated subjects

Study Device	VerTouch™
Duration of Device Exposure	< 2 hours
Reference Therapy	Conventional palpation technique used for spinal needle placement
Endpoints	
Primary Endpoint:
 
The number of insertion attempts (any forward movement of the needle following puncture of the skin) in the study device group as compared to the control group (palpation). Attempts are counted until confirmation of spinal canal access can be assessed.
 
Secondary Endpoints:
 
 1. Incidence of first-insertion success (a case that does not require any reinsertions, but can include any number of redirections) 2. Number of redirections (any forward movement of the

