3.5 Insertion

The Needle Guide is reversibly attached to the top (cranial side) of the Applicator, and its location is presented as a crosshair overlay in the imaging screen. Once an insertion site is identified, the user slides the Applicator until the crosshair aligns with that site. If a marking workflow has been selected, the user places the Marker directly through the exposed Marker Guide. He/she then removes the Device, and injects LA and inserts his/her preferred needle on the mark. For the placement workflows, LA is first injected directly through the Needle Guide. For introducer placement, the user then places the introducer through the Needle Guide. The Gate is then opened, which allows the Device to be removed from the partially placed introducer. Following Device removal, the introducer is fully inserted and the preferred spinal needle is placed through it. The same is done for needle placement; however, to ensure the needle does not exceed a safe depth while the device is in place, the earlier-described Restrictor is used. The Restrictor is pushed over to align with the Needle Guide for placement of a 3.5" needle; and it is further pulled up for placement of a 5" needle (**Figure 4**). Locking mechanisms ensure the Restrictor locks in both positions.

[figure not shown]

Figure 4. Side view (cranial) of VerTouch Needle Guide, depicting Restrictor configurations for safe placement of an introducer, and 3.5" and 5" needle, extracted from the IFU^[24].

After needle placement, the Gate is opened to allow the device to be pulled away from the introducer or needle. This is accomplished by sliding the Device downward, craniocaudally; and then leftward, mediolaterally (as viewed against the patient's back).

With any workflow, the ability of the system to assist with accurate insertion-site identification has the potential to be associated with a reduction in insertion attempts, although some redirections may still be necessary considering the fixed, perpendicular orientation of the Needle Guide. All Needle and Marker Guide interactions are performed with the right hand, per standard needle insertion training, regardless of handedness.

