6.3.2 Secondary Clinical Endpoint(s)

1. Incidence of first-insertion success (a case that does not require any reinsertions, but can include any number of redirections)
2. Number of redirections (any forward movement of the needle in a new direction not preceded by withdrawal from the skin, counted until confirmation of spinal canal access can be assessed)
3. Number of passes (any forward movement of the needle, calculated as the sum of insertions and redirections)
4. Incidence of first-pass success (a case that does not require reinsertions or redirections)
5. Subject discomfort during landmarking on a 100mm VAS (See Section 17.1)

6. Provider confidence with the identified insertion site on a 1-5 Likert scale (See Section 17.2)
7. Procedure success as confirmed by the following procedure-specific methods:
 - Epidural anesthesia: able to achieve a T10 or greater bilateral sensory level change to cold
 - Spinal anesthesia: able to achieve sensory blockade to surgical stimulus at level desired
 - Diagnostic and therapeutic LP: return of CSF
 - Blood patch: able to inject homologous blood into epidural space (entry confirmed by loss-of-resistance)

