- VerTouch workflow followed (N/A (control group), marking, introducer placement, needle placement)
- Calculation of number of re-insertions (1 less than insertions)
- Incidence of first-insertion success (1 insertion, any number of redirections)
- Calculation of number of passes (sum of insertions and redirections)
- Incidence of first-pass success (1 pass)
- Calculation of localization, insertion, and procedure times (based on start and end times)
- Incidence of traumatic tap
- Incidence of referral to radiology
- Incidence of conversion from spinal to epidural (neuraxial anesthesia only)
- Incidence of paresthesia (neuraxial anesthesia only)
- Incidence of PDPH
- Intensity of PDPH (mild, moderate, severe)
- Incidence of unintended dural puncture (epidural anesthesia only)
- Subject Discomfort Assessment
- Provider Confidence Assessment
- Adverse Event Assessment
- Upload of data from VerTouch

Post-procedure, the subject will be monitored for adverse events, adverse device effects or other reportable observations to ensure safety, entering relevant data into the eCRF. At the conclusion of the visit, the subject will be released and considered complete. After each procedure, imaging data from VerTouch will be uploaded by the designated observer to a study portal to support investigation of any anomalous finds and/or establishment of a human image database.

7.4.2 Visit 2

Visit 2 must occur at 3 ± 2 days following Visit 1. Phone, or other appropriate follow-ups will be made at Visit 2 to assess the presence and intensity of PDPH in subjects, and assess potential adverse events. At the conclusion of Visit 2, a Subject Study Exit CRF will be completed.

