8.3.4 Secondary and Tertiary Efficacy Endpoints

If that analysis reaches statistical significance, the hypotheses of the secondary variables found in section 8.2 will be considered sequentially such that if one analysis is statistically significant, then the next hypothesis can be evaluated to control for the Type I. The endpoints for these analyses are:

- Incidence of first-insertion success (a case that does not require any reinsertions, but can include any number of redirections)
- Number of redirections (any forward movement of the needle in a new direction not preceded by withdrawal from the skin, counted until confirmation of spinal canal access can be assessed)
- Number of passes (any forward movement of the needle, calculated as the sum of insertions and redirections)
- Incidence of first-pass success (a case that does not require reinsertions or redirections)
- Subject discomfort during landmarking on a 0-10 numeric rating scale (NRS)
- Provider confidence with the identified insertion site on a 1-5 Likert scale
- Procedure success as confirmed by the following procedure-specific methods:
 - Epidural anesthesia: able to achieve a T10 or greater bilateral sensory level change to cold
 - Spinal anesthesia: able to achieve sensory blockade to surgical stimulus at level desired
 - Diagnostic and therapeutic LP: return of CSF
 - Blood patch: able to inject homologous blood into epidural space (entry confirmed by loss-of-resistance)

The analysis methods are outlined Section 8.2 above.

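### The primary endpoint's written definition also captures every redirection, contradicting the plan's own rules for first-insertion success, re-insertions and passes

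*Protocol*

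**What the plan says.** The protocol synopsis and Protocol 6.3.1 give the only express definition of the primary variable: "The number of insertion attempts (any forward movement of the needle following puncture of the skin"), counted until spinal canal access can be assessed.

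Protocol 6.3.2 defines two neighbouring counts. A redirection is "any forward movement of the needle in a new direction not preceded by withdrawal from the skin". The pass count is "Number of passes (any forward movement of the needle, calculated as the sum of insertions and redirections").

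The derivation rules appear in Protocol 7.4.1 (Post-Treatment) and SAP 8.3.4:

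- "Calculation of number of re-insertions (1 less than insertions")
- "Incidence of first-insertion success (1 insertion, any number of redirections")
- the SAP equivalent, "Incidence of first-insertion success (a case that does not require any reinsertions, but can include any number of redirections")

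Protocol 6.1 and 7.4.1 have a designated study observer record insertions and redirections as separate items. Protocol 8.2.2 and SAP 8.3.3.2 make total insertions per subject the analysis variable. SAP 8.3.3 states the aim in terms of insertion attempts and does not define them.

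**The concern.** A needle that has not been withdrawn from the skin has already punctured it. Every redirection is therefore a forward movement after skin puncture and meets the written definition of an insertion attempt. Read that way, the primary endpoint almost coincides with the secondary pass count, and the derivation rules cannot hold.

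The endpoint is counted live by a study-team observer in each setting of an open-label trial. An observer who follows the written definition adds redirections to the primary count; one who follows the derivation rules does not. A mixture may not be separable afterwards. A record of 3 insertions and 2 redirections could mean one skin entry (written definition) or three (derivation rules).

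The error need not be equal between arms, because Protocol 3.5 anticipates "a reduction in insertion attempts, although some redirections may still be necessary considering the fixed, perpendicular orientation of the Needle Guide". First-insertion success and number of passes, first and third in the sequential testing order, use the same count.

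**Working it through.** **1. The rules side by side.** Take one skin puncture followed by two redirections.

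| Quantity | Written definition (6.3.1) | Derivation rules (6.3.2, 7.4.1, SAP 8.3.4) |
|---|---|---|
| Insertions | 1 + 2 = 3 | 1 |
| Re-insertions (insertions − 1) | 3 − 1 = 2 | 1 − 1 = 0 |
| Redirections | 2 | 2 |
| Passes (insertions + redirections) | 3 + 2 = 5 | 1 + 2 = 3 |
| First-insertion success (exactly 1 insertion) | No | Yes |

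The needle made three forward movements. The written definition reports five passes because each redirection is counted twice. It also turns a first-insertion success into a failure.

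**2. The plan's own power figures.** For first-insertion success, 50% against 81% with 48 per group at two-sided 0.05 gives 90.4%, which reproduces the stated 90%. For the primary endpoint the plan gives power only at 24 per group (at least 92% by bootstrap, 89% by t-test), from a simulation whose mixture parameters are not reported. A mixture fitted near the same means and SDs gave about 88–89% and 86%: close, but not an exact reproduction. Neither figure is disputed here.

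**3. Primary power at 48 per arm under the intended count.** Inputs from Protocol 6.4.1: palpation mean 2.1, SD 1.5; VerTouch mean 1.1, SD 0.6; one-sided 0.025.

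- Difference = 2.1 − 1.1 = 1.0
- Standard error = √[(1.5² + 0.6²)/48] = √[(2.25 + 0.36)/48] = 0.233
- Noncentrality = 1.0/0.233 = 4.29; Welch power = 98.8%

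**4. The same test if redirections enter the count.** The documents give no redirection rates, so the rates here are assumptions. If redirections are Poisson with rate r in both arms and independent of insertions, the difference stays at 1.0 and r is added to each variance:

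standard error = √[(2.25 + 0.36 + 2r)/48]

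| r per case, both arms | Standard error | Noncentrality | Welch power | Simulated bootstrap power |
|---|---|---|---|---|
| 0 | 0.233 | 4.29 | 98.8% | 98.5% |
| 0.5 | 0.274 | 3.65 | 94.9% | 95.4% |
| 1.0 | 0.310 | 3.23 | 89.0% | 91.6% |
| 2.25 | 0.385 | 2.60 | 72.9% | 76.1% |

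The bootstrap is the planned test. It was run on 1,500 simulated trials with 1,000 resamples each, with counts of 1 plus a negative binomial matched to the planning means and SDs. Success meant that the 97.5th percentile of the mean difference was below zero.

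**5. Unequal rates.** Starting from r = 0.5, 1.0 and 2.25, bootstrap power is:

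- with 0.5 more redirections per case under VerTouch: 44.0%, 34.9%, 24.9%
- with 0.5 more per case under palpation: 99.8%, 99.5%, 96.7%

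The documents do not say which arm would have more.

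**6. Dependence on the assumed distribution.** With geometric rather than Poisson redirections and equal means of 1, 2 and 3 per case, simulated bootstrap power at 48 per arm was about 74%, 43% and 24%.

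**The case against.** The best reply is that the intended meaning is plain from the whole text. Read together, 6.3.1 and 6.3.2 contrast an advance that begins with a puncture and an advance made without leaving the skin. The rule in 7.4.1 of one insertion with any number of redirections is impossible under the broad reading. Protocol 3.5 and 9.2.1 treat the two events as different, the observer records them separately, and the SAP does not repeat the broad definition. A counting rule may also exist in the treatment flowchart (Figure 6, not reproduced in the text reviewed), the Instructions for Use, the eCRF or the training material.

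Much of this stands. The intent is recoverable, the SAP's own rules agree with one another, and observers may have been given a correct rule. But no readable section says that an insertion is a separate skin entry, and the one express definition is broad enough to include redirections. Recording redirections separately does not settle whether they also enter the insertion count. A correct instruction elsewhere would still conflict with the protocol text.

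The objection to the power figures also stands in part. They rest on assumed rates, on redirections being independent of insertions, and on every observer counting literally. The negative binomial used for VerTouch also implies about 95% first-attempt success, against the 90% in the planning data. They show that the reading matters; they do not forecast a loss.

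One gap lies outside this point. A partial withdrawal and re-advance along the same track is a forward movement, and so a pass by its description. Once insertions are tied to skin entries, it is neither an insertion nor a redirection.

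**Conclusion.** The concern holds. Followed as written, the definition gives a wrong primary count and a wrong first-insertion result whenever a redirection occurs, and it contradicts rules stated elsewhere in both documents. That conclusion rests on the text alone.

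The practical size is unknown because no redirection rates are given. At assumed equal Poisson rates of 0.5 to 2.25 per case, with all redirections counted, primary power falls from about 99% to between 95% and 73% (Welch). It would be lower if VerTouch had more redirections than palpation, and higher if palpation had more. The false-positive rate is not inflated and the sample size is not in question. This is a wording inconsistency in the primary endpoint that should be corrected; the design itself is sound on this point.

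**What to change.** In the synopsis, Protocol 6.3.1 and SAP 8.3.3, define an insertion attempt as each separate entry through the skin by the procedure needle, or by the introducer through which it is passed, including the first entry. State that a forward movement in a new direction without withdrawal from the skin is counted only as a redirection. Insertions and redirections are then disjoint, no redirection is counted twice in the passes, and the first-insertion and re-insertion rules in 6.3.2, 7.4.1 and SAP 8.3.4 can stay as they are.

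Two optional additions would close the remaining edges. First, say that continued advance in the same track after device removal belongs to the same insertion, in line with Protocol 3.2. Second, say how a re-advance along the same track without leaving the skin is counted.

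The cost is one definition in three places and a matching line in the observer's counting instructions, settled before enrolment. No extra subjects, data or analyses are needed, and the sample size and power are unchanged.

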6.3.2 Secondary Clinical Endpoint(s)

1. Incidence of first-insertion success (a case that does not require any reinsertions, but can include any number of redirections)
2. Number of redirections (any forward movement of the needle in a new direction not preceded by withdrawal from the skin, counted until confirmation of spinal canal access can be assessed)
3. Number of passes (any forward movement of the needle, calculated as the sum of insertions and redirections)
4. Incidence of first-pass success (a case that does not require reinsertions or redirections)
5. Subject discomfort during landmarking on a 100mm VAS (See Section 17.1)

6. Provider confidence with the identified insertion site on a 1-5 Likert scale (See Section 17.2)
7. Procedure success as confirmed by the following procedure-specific methods:
 - Epidural anesthesia: able to achieve a T10 or greater bilateral sensory level change to cold
 - Spinal anesthesia: able to achieve sensory blockade to surgical stimulus at level desired
 - Diagnostic and therapeutic LP: return of CSF
 - Blood patch: able to inject homologous blood into epidural space (entry confirmed by loss-of-resistance)

6.3.3 Tertiary Endpoints

1. Localization time (time from first touch of draped patient to identification of an insertion site; for VerTouch, this is the time from device placement to movement of the applicator to the identified insertion site)
2. Insertion time (time from retrieval of marker or LA assembly until no further needle advancements are made)
3. Number of bone contacts (counted until confirmation of spinal canal access can be assessed)
4. Incidence of referral to radiology

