3.3 Device Placement

With VerTouch, users continue to use standard landmarking techniques to identify a safe level for the procedure area. This is typically done by palpating for the tips of the iliac crest, which approximately align with the L4-5 interspinous space. This is performed prior to draping the patient, such that the procedure area is exposed and used to guide Device placement. After Device assembly, the user then grips the Handle on the Base with his/her left hand, and places the assembled Device against the patient's back. Midline indicators on the Device can be used to support alignment with the midline of the spine. A rubber Bottom Pad on the Base prevents slippage of the Device along the back during use.

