8.2.3 Additional Analyses

The tertiary and exploratory endpoints will be summarized descriptively. Tertiary endpoints of localization time, insertion time, and number of bone contacts will also be evaluated for homogeneity of the group results using a Mann-Whitney test. The exploratory endpoint of procedure time will also be evaluated with a Mann-Whitney test. The tertiary, safety, and exploratory incidence endpoints will be evaluated for homogeneity of the rates across the treatment groups using likelihood ratio tests.

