9.2.1 Anticipated Risks / Risk Mitigation

As discussed, neuraxial procedures have long been associated with concerns of uncertainty and subjectivity. VerTouch is designed to integrate into the existing clinical workflow and environment; and to offer additional information in support of these procedures, with greater objectiveness than palpation, and greater interpretability than ultrasound.

IntuiTap has performed risk analyses in accordance with ISO 14971:2019, IEC 62366:2015, IEC 62304:2006, and IEC 60601-1, from which the following categories of anticipated VerTouch risks have been identified:

- Failure to support proper identification of an insertion site (e.g. generates scanning output that is not uniform, aligned, or sufficiently sensitive)
- Failure to support proper needle insertion (e.g. provides marker or needle guidance that is not accurate, precise, or intuitive)
- Tissue trauma (e.g. causes needle dragging, or excessive levels of sustained force)
- Standard risks associated with electromechanical medical devices (e.g. is not biocompatible, sterile, or electrically safe)

The first two categories could be associated with an increase in procedure time and/or an incorrect needle insertion. In nearly all indications, added time would not result in serious harm. If occurring in emergent cases, particularly in labor/delivery where the opportunity to administer anesthesia could be missed, the provider could revert to the manual procedure. In general, the consequence of an incorrect insertion associated with VerTouch would be identical to that with the standard of care. Namely, it would warrant reinsertions and/or redirections, which can be associated with certain adverse events that are possible in any neuraxial procedure, as listed in Section 9.3, most of which are very rare and/or have low prevalence. Among these, more severe harm exists in epidural and intrathecal injections, where incorrect insertion can result in incorrect administration of a drug or anesthetic.

All risks belonging to the above categories will be reduced as far as possible via safety by design, protective measures, and information for safety. To mitigate the risk of device failure, design verification will be completed, including bench, usability, and standards testing, prior to study execution. Labeling will be provided to ensure proper use of all VerTouch components.

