8.3.5 Other Statistical Analyses

There will also be several tertiary and exploratory endpoints examined in this study. The tertiary endpoints are as follows:

- Localization time (time from first touch of draped patient to identification of an insertion site; for VerTouch, this is the time from VerTouch device placement to movement of the applicator to the identified insertion site)
- Insertion time (time from retrieval of marker or LA assembly until no further needle advancements are made)
- Number of bone contacts (counted until confirmation of spinal canal access can be assessed)
- Incidence of referral to radiology

Exploratory endpoints:

- Procedure time (from positioning of the patient to removal of the drape from the subject's back)
- Incidence of conversion from spinal to epidural (specific to neuraxial anesthesia)

The tertiary and exploratory endpoints will be summarized descriptively. Tertiary endpoints of localization time, insertion time, and number of bone contacts will also be evaluated for homogeneity of the group results using a Mann-Whitney test. The exploratory endpoint of procedure time will also be evaluated with a Mann-Whitney test. The tertiary and exploratory incidence endpoints will be evaluated for homogeneity of the rates across the treatment groups using likelihood ratio tests.

Client/Project	IntuiTap/VerTouch
Version and Date	V02 – 22 December 2020

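### Localization time starts and stops on different events in the two arms, with no rule for reversion or rescanning, so the Mann-Whitney comparison can be biased in a direction the documents do not settle

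*Protocol*

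**What the plan says.** The general definition in SAP 8.3.5 is "time from first touch of draped patient to identification of an insertion site". It is followed at once by a device-specific one: "for VerTouch, this is the time from VerTouch device placement to movement of the applicator to the identified insertion site". Protocol 6.3.3 has the same pair, the second part reading "for VerTouch, this is the time from device placement to movement of the applicator to the identified insertion site", and so does the synopsis.

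Other sections bear on how these clocks run:

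- **Before the VerTouch start.** Protocol 3.3 puts iliac-crest landmarking before draping. It then says "After Device assembly, the user then grips the Handle on the Base with his/her left hand, and places the assembled Device against the patient's back". Assembly therefore precedes the start event. Protocol 7.4.1 has initial level-finding done the same way in both groups.
- **The VerTouch stop.** In Protocol 3.5 the applicator is slid to the site once the site has been identified.
- **Rescanning.** Protocol 3.4 lets the user reset the image and scan elsewhere if alignment is poor or no space is seen.
- **Reversion.** In discussing lost time in emergent cases, Protocol 9.2.1 says "the provider could revert to the manual procedure".
- **Analysis.** Protocol 8.2.3 states: "Tertiary endpoints of localization time, insertion time, and number of bone contacts will also be evaluated for homogeneity", by a Mann-Whitney test. SAP 8.3.5 agrees. All results use the ITT population (Protocol 8.1) and whatever data are available (Protocol 8.2). Best- and worst-case imputation is listed only for the primary endpoint (Protocol 8.2.2, SAP 8.3.3.3).

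**The concern.** A rank test of times assumes that both arms measure the same interval. Here a hand on the draped back starts the general clock, but only device placement starts the VerTouch clock. The general clock stops when a site is found by any means, whereas the VerTouch clock stops on a mechanical step that belongs to one technique.

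The stop event matters most. A VerTouch subject whose provider goes back to palpation stays in the VerTouch arm under ITT, but the applicator is never moved to a chosen site. Protocol 7.4.1 calculates localization time from start and end times, so without an end time there is no value to analyse. If such cases are slow, the VerTouch distribution loses part of its upper tail.

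What is at stake is the credibility of one reported comparison. Protocol 2.1 lists more standardized localization and insertion times among the device's potential benefits, so the result is likely to be read.

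**Working it through.** **Step 1: is there a figure to reproduce?** No. Neither document gives an expected localization time, an SD, a reversion rate or a power statement for this endpoint.

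**Step 2: the clocks side by side.**

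| | General (palpation) | VerTouch | Likely effect of the difference |
|---|---|---|---|
| Start | First touch after draping | Device placement | None if placement is the first touch; otherwise VerTouch looks shorter |
| Stop | Site identified | Applicator moved to the identified site | VerTouch looks longer |
| Rescan | Not applicable | No rule on restarting | Shorter if restarted, none if not |
| Reversion to palpation | Not applicable | Stop event never occurs | Depends on which cases are lost |
| No site found | No stop event | No stop event | Depends on the arm and number |

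The table contains effects of both signs. The device log does not settle the rescanning question, because Protocol 3.7 has it keep the final scan only.

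**Step 3: what could the effects amount to?** An illustrative simulation used 48 per arm (Protocol 6.4.1), identical true lognormal times in both arms and 4,000 trials per scenario. A false finding is a one-sided Mann-Whitney p below 0.025 in VerTouch's favour. The log-SD is √ln(1 + CV²), which is 0.47 at CV 0.5 and 0.83 at CV 1.0. The CVs, offsets and numbers lost are all assumptions.

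| Scenario | CV 0.5 | CV 1.0 |
|---|---|---|
| Same clock | 2.9% | 2.7% |
| VerTouch clock omits 10% of the median | 18% | 11% |
| omits 20% | 56% | 26% |
| omits 30% | 88% | 51% |
| Slowest 1 of 48 VerTouch cases has no value | 4% | 4% |
| slowest 2 | 6% | 6% |
| slowest 5 | 14% | 15% |
| slowest 7 | 23% | 23% |
| VerTouch stop later by 10% of the median | 0.1% | 0.4% |

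**Step 4: do opposite effects offset each other?** Assume a median of 90 s and log-SD 0.6, and count two-sided p ≤ 0.05 with the VerTouch median lower. Losing the 3 slowest VerTouch cases gives about 7.5%. Adding 5 s for the later VerTouch stop brings this back to about 3%, close to nominal. With 15 s untimed at the start and 3 cases lost, the rate is about 52%, and the same 5 s reduces it to about 34%. The net result depends on quantities that the documents do not give.

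**The case against.** A reader might infer that the definition favours VerTouch. The documents do not support that, for these reasons:

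- **Start.** The device clause can be read as explaining the general clock. Level-finding comes before draping, and no hand palpation of the draped back before placement is described, so placement may well be the first touch. This stands, although the text does not say so. The scenarios with untimed seconds at the start therefore rest on a step that is not documented. The treatment flowchart (Protocol Figure 6) could not be read for this check.
- **Stop.** The VerTouch clock stops after identification, which works against VerTouch. This stands.
- **Reversion.** It is mentioned for emergent cases. For poor imaging the described response is to rescan. Protocol 6.1 has the observer record the time to identify a site without distinguishing arms, so a reverted case might still be timed. An emergent case might also be abandoned early and so not be among the slowest. This stands as to direction and frequency. It does not supply the missing rule, and labor is an eligible procedure (Protocol 6.4.5).
- **Palpation can also lack a stop.** If no site is found and the patient goes to radiology, the general clock has no end either. Loss of slow cases is not confined to one arm. This stands.
- **Assembly.** Leaving device set-up out of localization time is a reasonable definition. This stands.
- **Weight.** Localization time lies outside the primary test and the seven-step secondary sequence. Protocol 8.2 and SAP 8.1 keep tertiary p-values out of labeling. Procedure time runs on one clock in both arms and is also tested. This stands, although procedure time runs from positioning to drape removal and cannot isolate localization.

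**Conclusion.** The defect is in the text. The two arms have different start and stop events for a quantity that is then compared between them. The VerTouch stop cannot occur after reversion, and rescanning has no timing rule. Bias is possible, and some of it could come from selective loss of cases. Its sign and size cannot be derived from the documents. The simulated rates run from 0.1% to 88% against a nominal 2.5%, depending wholly on assumed inputs, so they show sensitivity only and do not estimate this trial's error.

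The consequence is limited to the interpretation of one tertiary comparison. The primary result and the labeling claims are not touched. The change is still worth making before enrollment, because seconds that were not timed cannot be recovered afterwards.

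**What to change.** Use one definition in Protocol 6.3.3, the synopsis and SAP 8.3.5:

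- **Start** at the first touch of the draped back, by hand or device.
- **Stop** when the provider declares the insertion site, by whatever technique.
- **Keep the clock running** through rescanning and through any reversion to palpation, and analyse these subjects in their allocated arm.
- **If no site is identified, in either arm,** rank the case as a longest time instead of dropping it. The Mann-Whitney test takes tied worst ranks, so no numerical value need be invented. Report the number of such cases by arm.

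Recording device assembly time as a separate item is optional.

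The cost is wording in three places and a clear instruction to the observer, who already records these times. VerTouch times may look slightly longer where the device was not the first touch or where the provider reverted.
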